4 STUDY DESIGN

4.1 General Description

This study is a multi-center, randomized, open-label clinical trial evaluating the efficacy and safety of ESG as an adjunct to life-style intervention for weight loss and improvement in obesity-related co-morbidities compared to lifestyle intervention alone in participants with a BMI ≥ 30 and ≤ 40 kg/m² who have failed to achieve and maintain weight loss with a non-surgical program.

Participants will be recruited from outpatient clinical weight loss clinics and from study-related institutional review board (IRB) approved advertisements. The cohort will include nor more than 50 patients without at least one of a) hypertension (HTN) on one or more anti-hypertensive medications or b) type II diabetes mellitus (DM) on oral agents only with HbA1c ≤ 9 . Enrollment will be tracked continuously and enrollment closed to non-DM, non-HTN patients after meeting the target for that group.

Two hundred eligible participants will be stratified into three groups (obesity, obesity-hypertension, and obesity-diabetes) and then block-randomized 1 to 1.5 to treatment (80 participants) and control (120 participants) groups alone as depicted in the diagram on page 16. All treatment group participants will undergo endoscopy and those without endoscopic contraindications will undergo the ESG. All control subjects will follow a low-calorie, healthy lifestyle intervention only for 12 months. After 12 months of lifestyle intervention, eligible control participants will crossover to receive the ESG. Those who had the ESG will undergo a repeat upper endoscopy at 52 weeks +- 4 weeks to evaluate the durability of the plications and re-tighten the ESG if needed with continued follow-up for 12 additional months.

The study will have two levels:

1. Level 1: the randomized study phase with primary outcomes for both groups evaluated at 12 months
2. Level 2: the crossover, non-randomized study phase with outcomes for a) the initial treatment group at 24 months post ESG (12 months after the re-tightening procedure) b) for the controlled cross-over group evaluated at 12 months after ESG

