4.2 Endpoints

4.2.1 Effectiveness

Primary:

- % EWL at 12 months from randomization by randomized arm measured at the week 52 visit. The null hypothesis is no difference in mean %EWL between randomized arms.

Secondary:

- Proportion with $\geq 25\%$ EWL at 12 months by randomized arm
- Change in hypertension in the ESG group compared to LS only

- Proportion of patients off or with reduction in their antihypertensive medications in the randomized control arm compared to lifestyle control at 12 months
- Change in systolic and diastolic blood pressure in the randomized arm compared to lifestyle control at 12 months
- Comparing diastolic and systolic blood pressures as continuous variables 12 months after ESG (compared to baseline) in the entire cohort that received ESG both in the randomized and cross-over segments of the trial
- Change in type II diabetes in the ESG groups compared to LS only
 - Proportion of patients off or with reduction in their diabetes medications in the randomized arm compared to lifestyle control at 12 months
 - Change in HgbA1c in the randomized arm compared to lifestyle control at 12 months
 - Comparing HgbA1c as a continues variable 12 months after ESG (compared to before) in the entire cohort that received ESG both in the randomized and cross-over segments of the trial.
- %TBWL in the ESG group compared to LS only
- % of patients in the ESG group achieving > 5% TBWL compared to LS only
- % of patients in the ESG group achieving > 10% TBWL compared to LS only
- Durability of the plication evaluated by endoscopy at 12 months (level 1) and effectiveness of re-tightening procedure performed at 12 months (level 1) in maintaining and / or enhancing weight loss at 24 months. Durability of the plication and procedure is defined as greater than 70% of the cohort undergoing repeat endoscopy achieving a score of ≥ 1 out of 3 prior to re-tightening (Grading system and evaluation in appendix). Efficacy of re-tightening is defined as $\geq 50\%$ of the cohort undergoing the re-tightening maintaining or losing weight compared to the re-tightening weight at 12 months after the re-tightening procedure.
- Incidence of esophagitis at repeat endoscopy at 12 months (level 1). (LA grading system in form in appendix)
- Changes in quality of life assessed using standard validated questionnaires (IWQOL-lite and SF-36)
- Changes in depression assessed using PHQ-9 questionnaire

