5.5 Trial Intervention

5.5.1.1.1 Control group

Participants randomized to the control group (lifestyle intervention only) in Level 1 will undergo a standard moderate intensity life-style intervention during the first 12 months of Level 1. The first dietary visit will be scheduled on the day of randomization. A low-calorie diet plan will be reviewed with each participant and will be adjusted according to each participant's needs. Participants in the control group will not undergo the liquid transitional diet as it is difficult to achieve compliance without intervention. Physical activity, including 150 minutes of aerobic exercise per week, will be encouraged and assessed for compliance during the study. Participants will have 12 follow-up visits in the 12 months of Level 1 as described in the schedule of events. Participants will receive \$100 for every 4 visits they attend consecutively in Level 1 with the ability to earn a maximum of \$300 at the end of the first 12 months of Level 1.

Control group participants who were compliant with at least 75% of visits in the first 12 months of Level 1, have not achieved $\geq 25\%$ EWL measured at the week 52 visit, or still have a BMI ≥ 30 and ≤ 40 , and have no new psychosocial contraindications as deemed by the treatment team to the procedure will cross over to receive ESG in Level 2, in addition to the standard moderate intensity lifestyle intervention program for 12 months. After crossing over into Level 2, participants will be able to earn the same remuneration as in Level 1 (\$100 for every 4 consecutive visits attended). Those who were compliant with attending 75% of the visits in Level 2 (second 12 months) will receive a bonus of \$300 at the final study visit, for a potential total of \$900 earned in the two years.

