5.5.1.1.2 Treatment Group

ESG is an endoluminal procedure similar to sleeve gastrectomy targeting the shape of the stomach. The targeted shape is tubular gastric body with a small pouch in the fundus. A step-by-step video circulated to all sites and a mandate to have the proctor present for the first case were done to ensure conformity to the technique. The same expert endoscopist will proctor all sites. In general, the technique involves 7-9 bites in a running O shaped pattern that is repeated 4-5 times in the stomach to achieve the desired shape. Proximally, it might be difficult to do the O sequence; thus, the operator can do triangular 3-4 bites interrupted suturing sequence. Each O sequence can be enforced by a layer of triangular interrupted suture. All bites are intended to be full thickness with the aid of tissue helix. The re-enforcing bites can be submucosal. The sequence is staggered to avoid gaps. In general, sutures used is limited to 10. ESG narrows the stomach axially and reduce its length longitudinally.

Participants assigned to the treatment group will report to the procedure suite within 30 days of randomization. Participants of child-bearing potential will be required to have a pregnancy test within 7 days of the scheduled ESG. Participants taking medications for hypertension and/or type II diabetes will be instructed to notify their prescribing physician of their procedure and to discuss any necessary medication changes for the post-op period.

The ESG is done in the outpatient setting. Within two hours prior to ESG, IV access will be obtained, IV hydration initiated, and a transdermal scopolamine patch placed for patients 50 years of age or younger (this will be removed in 24 to 48 hours after the procedure).

Prior to ESG, a standard upper endoscopy is performed to rule out any contraindicating findings. All ESG procedures will be done under general anesthesia with endotracheal intubation and utilizing CO₂ insufflation. During the procedure, IV hydration will be continued and patients will be given the following: one dose of IV antibiotics (Zosyn, Ceftriaxone, or Ciprofloxacin), 8mg of IV Zofran, and 8mg of Decadron. A minimum of two liters of IV hydration (either normal saline or lactate ringers) should be administered in the perioperative recovery period before discharge. Sequential compression devices (SCDs) will be used perioperatively to decrease the risk of deep vein thrombosis (DVT) and pulmonary embolism (PE).

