ESG patients will undergo a standard moderate intensity life-style intervention administered over 12 visits in the first year after ESG. Participants will be required to follow up with their prescribing physician to make any necessary changes to their hypertension and/or type II diabetes medications at 3, 6, 9 and 12 months. Completion of patient follow-up with providers for medication adjustment will be captured with completion of the appropriate CRF at the corresponding visits. In the event that participants are unable to contact their physician or participants are experiencing symptoms related to the medication dosing requiring urgent action, the study team will make any necessary

changes in their medication dosing and document these changes appropriately in the relevant CRFs. Any medication changes will be monitored and recorded by the study team.

All ESG patients in Level 1 (80) will be evaluated for %EWL at the end of Level 1 (measurement of primary endpoint). Those ESG patients who have achieved >25% EWL at the end of Level 1 will not undergo a repeat endoscopy and will continue to follow-up with a lifestyle intervention in Level 2. Those ESG patients who have not achieved >25% EWL at the end of Level 1 will undergo a repeat upper endoscopy at 52 to 60 weeks to assess the durability of the plications (see Plication Durability form), and perform a retightening of the ESG if needed. The need for re-tightening will be determined by the PI after evaluating the sutures based on a grading system presented in the retightening CRF. The retightening procedure will be performed if at least one of the three portions (proximal, mid, and distal) of the endoscopic sleeve is non-tubular in shape. For each tubular third of the sleeve, 1 point will be given. A score of 3/3 means the entire (proximal, mid, and distal) sleeve is tubular in shape. A score of 2/3 means that one-third of the sleeve is no longer tubular. A score of 1/3 means that two-thirds of the sleeve are no longer tubular. Finally a score of 0/3 means the entire sleeve is no longer tubular. Re-tightening will occur for patients with a score of 0, 1 or 2.

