TABLE 2. MERIT SCHEDULE OF EVENTS (Year 2, Level 2, Treatment Group, 80 Patients)							
	ESG retightening [†]	Post-Op Clinical Eval ^{**}	Follow-up after ESG retightening OR Week 60 [†]	Week 72-76*	Weeks 80, 88, 96	Week 104 (Final Year 2 visit)	Unscheduled Visit
Visit Number	17	-	18	19	20, 21, 22	23	
Informed consent							
Complete Physical Exam (CPE) by Investigator or Investigator delegated / medically qualified team member				X		X	X
Investigator or Investigator delegated/medically qualified team member exam			X	X	X	X	X
EKG if (> 50 yo)							
Formal nutritional assessment							
Formal psychology evaluation							
Pregnancy test (females of childbearing potential only)							
Laboratory tests ^{**}				X		X	
Questionnaires [#]				X		X	
Inclusion/exclusion criteria							
Endoscopy / Procedure	X						
Procedure Assessment Form	X						
GERD Questionnaire + Activity Assessment Form			X	X	X	X	
Weight, BMI/height, Waist and Hip Circumference Form	X		X	X	X	X	X
Vital Signs Form	X		X	X	X	X	X
Adverse Events Form		X	X	X	X	X	X
Medications Form ^{##}			X	X	X	X	X
Post-enrollment Nutrition / Exercise / satiety counseling and assessment			X	X	X	X	
Subject Satisfaction Questionnaire (study termination)						X	

** Electrolytes, Creatinine, CBC, Iron, TIBC, B12, 25-hydroxy Vitamin D, TSH, HgA1c, fasting blood sugar and insulin, PTT, fasting lipids profile (total cholesterol, LDL, HDL, and Triglyceride), ALT, AST, ALK-P, total bilirubin, direct bilirubin, BUN, total protein, albumin, CRP, urinalysis; also include PYY-1, GLP-1 and total Ghrelin pending sites' availability to analyze

IWFQOL-Lite, SF36, PHQ9, Pittsburg Sleep Quality Index (PSQI), Three factor eating questionnaire (TFEQ)

Record all medications including dose and frequency; especially diabetes and blood pressure medication.

++ Post-op phone call, no clinic visit, to occur between 18-36 hours post-op

+ ESG retightening to occur between Weeks 52-60 for those who qualify with in-clinic follow-up visit to occur 4 weeks post retightening, or subjects to continue to Week 60 for those who do not qualify for ESG retightening

*Lab draw to occur between Week 72-76

5.6.1.1.3 Schedule of Events for Control Group, Crossover in Year 1, Level 1

TABLE 3. MERIT SCHEDULE OF EVENTS (Year 1, Level 1, Control Group, 120 patients)									

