	Enrollment; Screening/ Baseline	Randomization / Week 1 visit	Weeks 4, 8	Week 12	Weeks 16, 20	Week 24 (6 month)	Weeks 30, 36, 42, 48	Week 52 (Final Year 1 visit), re-screen for crossover to ESG	Unscheduled Visit
Visit Number	-1	1	2,3	4	5,6	7	8,9,10,11,	12	
Informed consent	X								
Complete Physical Exam (CPE) by Investigator or Investigator delegated / medically qualified team member	X			X		X	X	X	X
Investigator or Investigator delegated/medically qualified team member exam		X ⁺⁺	X	X	X	X	X	X	X
EKG if (> 50 yo)	X							X	
Formal nutritional assessment	X								
Formal psychology evaluation	X								
Pregnancy test (females of childbearing potential only)	X								
Laboratory tests, H-pylori breath testing (baseline only)* *	X							X	
Questionnaires#	X			X		X		X	
Inclusion/exclusion criteria	X							X	
Endoscopy / Procedure									
Procedure Assessment Form									
GERD Questionnaire + Activity Assessment Form	X	X	X	X	X	X	X	X	
Weight, BMI/height, Waist and Hip Circumference Form	X	X	X	X	X	X	X	X	X
Vital Signs Form	X	X	X	X	X	X	X	X	X
Adverse Events Form		X	X	X	X	X	X	X	X
Medications Form##	X	X	X	X	X	X	X	X	X
Post-enrollment Nutrition / Exercise / satiety counseling and assessment		X	X	X	X	X	X	X	
Randomization to ESG vs. LS ⁺		X							
Subject Satisfaction Questionnaire (control phase)								X	

** Electrolytes, Creatinine, CBC, Iron, TIBC, B12, 25-hydroxy Vitamin D, TSH, HgA1c, fasting blood sugar and insulin, PTT, fasting lipids profile (total cholesterol, LDL, HDL, and Triglyceride), ALT, AST, ALK-P, total bilirubin, direct bilirubin, BUN, total protein, albumin, CRP, urinalysis; also include PYY-1, GLP-1 and total Ghrelin pending sites' availability to analyze

Eating disorder questionnaire + hospital anxiety and depression questionnaires (only at base-line), IWFQOL-Lite, SF36, PHQ9, Pittsburgh Sleep Quality Index (PSQI), Three factor eating questionnaire (TFEQ)

Record all medications including dose and frequency; especially diabetes and blood pressure medication.

+ LS start with the week 1 visit with no transitional diet.

++ Required only for Week 1 visit

5.6.1.1.4 Schedule of Events for Control Group, Crossover in Year 2, Level 2

[figure not shown]
TABLE 3. MERIT SCHEDULE OF EVENTS (Year 2, Level 2, Control Group, cross-over 120 patients)									
	ESG Procedure	Post-Op Phone Call	Weeks 1, 4, 8	Week 12	Weeks 16, 20	Week 24 (6 month)	Weeks 30, 36, 42, 48	Week 52 (Final Year 1 visit)	Unscheduled Visit
Visit Number	0	-	1,2,3	4	5,6	7	8,9,10,11	12	

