7.2.2 Secondary Aims

Continuous secondary outcomes, including change in systolic and diastolic blood pressure and change in HbA1c, QOL questionnaires such as the SF-36, PHQ-9, and eating behavior scores will be compared between treatment arms using ANCOVA with adjustment for the same variables specified in the primary analysis.

Binary outcomes, including proportion with $\geq 25\%$ reduction in %EWL and incidence of esophagitis will be compared between treatment arms by Pearson Chi-square test.

Among patients randomized to the treatment ESG group, the association between the durability of plication at repeat endoscopy (score ≥ 1 on EGD grading system) and number of sutures required for re-tightening with change in EWL from 12 months to 24 months will be assessed using linear regression with adjustment for BMI, %EWL between randomization and 12 month follow up, HTN status, and DM status. This is an observational comparison.

Among patients randomized to the control LS arm, the percent EWL from the 12 month assessment to the 24 month assessment will be measured. This percentage will be compared to percent EWL in the same group with lifestyle intervention only in the first 12 months using a one sample t-test.

Among all subjects, %EWL will be compared at 24 months between initial and delayed ESG. However, this is not considered a comparison of randomized arms as follow up is not continued for patients with $\geq 25\%$ EWL from LS at 12 months.

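### The between-arm chi-square test for esophagitis has no randomized comparator, and two sections disagree on which ESG patients are re-scoped

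*Combined protocol and SAP*

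**What the plan says.** - **Test.** Section 7.2.2, on binary secondary outcomes: "incidence of esophagitis will be compared between treatment arms by Pearson Chi-square test".
- **Endpoint.** Section 4.2.1 lists it as "Incidence of esophagitis at repeat endoscopy at 12 months (level 1"), graded by the LA system.
- **Control arm, Year 1.** Section 4.1 gives controls lifestyle intervention only for 12 months. In the Year 1 control table of section 5.6, the row "Endoscopy / Procedure" is blank at every visit, including week 52.
- **Control arm, crossover.** Section 5.5.1.1.2 says "Prior to ESG, a standard upper endoscopy is performed to rule out any contraindicating findings", so crossover controls are scoped before their ESG. Section 5.5.1.1.1 limits crossover to "Control group participants who were compliant with at least 75% of visits in the first 12 months of Level 1" who also meet a condition on EWL or BMI and have no new psychosocial contraindication.
- **ESG arm, rule A.** Section 4.1: "Those who had the ESG will undergo a repeat upper endoscopy at 52 weeks +- 4 weeks".
- **ESG arm, rule B.** Section 5.5.1.1.2: "Those ESG patients who have achieved >25% EWL at the end of Level 1 will not undergo a repeat endoscopy". The others are re-scoped at weeks 52 to 60.
- **Schedule.** The Table 2 footnote in section 5.6: "ESG retightening to occur between Weeks 52-60 for those who qualify".

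**The concern.** A chi-square test between arms needs a count of cases and non-cases in each arm. The endpoint is tied to a procedure that one arm does not have during the randomized phase. A listed secondary test would then have to be abandoned, or given a substitute comparator after the data are in.

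What remains is a single-arm rate, and the documents do not settle whose rate it is. If all ESG patients are re-scoped, it describes the arm. If only those without more than 25% EWL are re-scoped, it describes a group chosen by its 12-month weight loss. The two differ in precision and in meaning, and a reader of the results could not tell which was intended.

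**Working it through.** **Inputs.** 80 ESG and 120 LS patients; planning values of 25% EWL (SD 30) for ESG and 10% (SD 5) for LS; up to 20% of LS patients reaching 25% EWL and up to 20% lost before month 12 (all section 7.1). Reference BMI 25 for %EWL (section 2.3). Eligible BMI 30 to 40 (section 4.5). Published 12-month loss of 18% TBWL (section 2.2).

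**1. The plan's own figures.** The documents give no sample size for esophagitis. The section 7.1 figures that supply the mean and SD do reproduce. With 34 and 51 patients, SE = √(900/34 + 25/51) = 5.19 and 15/5.19 = 2.89; Welch power is 80.1%. With 45 and 68, SE = √(900/45 + 25/68) = 4.51 and 15/4.51 = 3.32; power is 90.2%. Controls expected to continue: 120 × 0.8 × 0.8 = 76.8, stated as 77.

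**2. The control row.** Controls with a scheduled Year 1 endoscopy: 0 of 120. That row of the 2×2 table is empty, its expected counts are zero, and Pearson's statistic is undefined.

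**3. Whether the crossover endoscopy can fill the row.**

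| | ESG repeat endoscopy | Control crossover endoscopy |
|---|---|---|
| Order | repeat, after ESG | first |
| Named in the endpoint | yes | no |
| Who is scoped | all ESG patients, or those without >25% EWL | selected on attendance and on EWL or BMI |
| Planned number | 80 or about 40 | at least 77 of 120 |

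The groups also differ in earlier screening. ESG patients had an endoscopy before the procedure, and those with contraindications did not proceed (section 4.1). Controls had no such check at randomization. Comparing the two columns is not a comparison of the arms as randomized.

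**4. The ESG denominator.**
- Rule A (section 4.1): up to 80.
- Rule B (section 5.5.1.1.2), assuming normality at the planning values: 80 × Φ((25 − 25)/30) = 80 × 0.50 = 40.
- With 20% loss (stated for LS, assumed here for ESG): 64 and 32.

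Direction of change under rule B: %EWL = %TBWL × BMI/(BMI − 25). If 18% TBWL held and every patient had BMI 40, the mean would be 18 × 40/15 = 48% EWL, and 80 × Φ((25 − 48)/30) = 17.7 would be re-scoped. At BMI 30 the mean would be 108% and the count 0.2. These two counts assume a single common BMI and carry SD 30 over to a different mean. They show only that the number falls below 40 if weight loss is better.

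**5. Precision.** For zero cases, the exact two-sided 95% upper limit is 1 − 0.025^(1/n):

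| n re-scoped | 80 | 64 | 40 | 32 |
|---|---|---|---|---|
| Upper limit | 4.5% | 5.6% | 8.8% | 10.9% |

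With 10% observed, the exact interval is 4.4% to 18.8% for 8 of 80 and 2.8% to 23.7% for 4 of 40.

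**The case against.** The strongest reply is that blank cells in the Year 1 control table prove little. The Year 1 table for the ESG arm shows no week-52 endoscopy either; its only endoscopy is the initial procedure, and the re-scope appears in the Year 2 table. The crossover endoscopy in controls is also a Year 2 event, following the week-52 visit, in a planned 77 or more patients. By that standard both arms have endoscopic findings from about the same time.

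This stands in part. A reader might infer that no control ever has endoscopic data, and that would be wrong. But the endpoint specifies a repeat endoscopy, nothing in the plan assigns the crossover findings to it, and the controls who would supply them are selected after randomization. The test as a randomized comparison is not rescued.

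A reader might also infer that only a handful of ESG patients would be re-scoped. The documents do not support a specific small number: they state no expected BMI, and the SD at a higher mean is unknown. Only 80 against about 40 rests on stated planning values.

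Two neighbouring points are not defects:
- **Omeprazole.** It is prescribed for 12 months from ESG, so the re-scope falls near or just after its end. That is part of the regimen, and the documents give no effect on the rate.
- **GERD questionnaire.** It is collected in both arms with no named analysis, but so are the sleep and satisfaction questionnaires. Section 7.2.3 allows unlisted analyses as exploratory, and the scoring is not shown.

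**Conclusion.** The point holds and is minor. Esophagitis cannot be compared between randomized arms with the endoscopies the plan schedules. That follows from the text alone and needs no assumption.

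The denominator conflict is also a matter of text. Its size, 80 against about 40, rests on the planning mean and SD and on normality; section 7.1 calls that mean conservative, so the second figure may be lower. Under section 5.5.1.1.2 the scoped patients are selected on low weight loss, and their rate should not be read as that of the ESG arm.

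A reader might take this as a weakness in the trial's main efficacy or safety conclusions. It is not. The primary endpoint, the SAE threshold and the four objectives in section 3 do not depend on this test.

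**What to change.** 1. In section 7.2.2, remove esophagitis from the outcomes tested between arms by chi-square.
2. Report it descriptively by LA grade among ESG patients actually re-scoped: number scoped out of number treated, number with esophagitis, and an exact 95% CI. State that under section 5.5.1.1.2 the rate applies only to patients without more than 25% EWL.
3. Where recorded, show the same patient's finding at the endoscopy before ESG. The exclusion criteria rule out only LA grades C and D, so milder esophagitis could already be present.
4. Align section 4.1 with section 5.5.1.1.2. The Table 2 footnote uses the same 52-to-60-week window and fits that rule, although it governs re-tightening rather than the endoscopy itself. This choice adds no endoscopy; adopting section 4.1's rule instead would add them for patients above 25% EWL.

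Optional only: list PPI status beside the esophagitis rate, or name an exploratory analysis of the GERD questionnaire.

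**Cost.** One edit to the analysis section, one to the protocol's design section, and one table from forms already collected. There would be no between-arm p-value for esophagitis, and the table may be small.

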7 STATISTICAL ANALYSIS

7.1 Power and Sample Size

The primary endpoint for power and sample size is %EWL at 12 months. The null hypothesis is no difference in mean %EWL between ESG and LS randomized arms ($H_0: \mu_t = \mu_c$ where μ_t is the average %EWL in the ESG group and μ_c is average %EWL in the LS group). We will perform a two-sided hypothesis test at alpha level 0.05 (alternative hypothesis $H_a: \mu_t \neq \mu_c$) Based on the published literature with the ESG technique a conservative presumption is 25% EWL in the ESG arm with a standard deviation (SD) of 30% at 12 months compared to 10% EWL on LS alone with SD of 5%. We plan a 1:1.5 randomization scheme that allocates 3 patients to LS for every 2 to ESG at the time of randomization. Based on a two-sample t-test with unequal variances and two-sided alpha=0.05, we would have 80% power to detect a difference of 15% in average %EWL between groups with 34 patients allocated to ESG and 51 randomized to LS. 90% power would require group sizes of 45 and 68, respectively. To allow for dropout, and more importantly, to power exploratory aims for obesity comorbidity subgroups, we propose the initial randomization of 200 patients – 80 to ESG and 120 to LS.

120 subjects are initially randomized to LS in level 1. Of these, we anticipate up to 20% will achieve a successful decrease of $\geq 25\%$ in %EWL through LS alone at 12 months. Further, we anticipate up to 20% may be lost to follow up or drop out prior to 12 month follow up. Thus, we anticipate at least 77 ($120 * 0.8 * 0.8$) subjects to continue to level 2 and be offered ESG. We will test the one-sample hypothesis (non-randomized) that of those offered ESG at 12 months, average change in %EWL will be at least 10%. Based on a one-sample t-test with two-sided alpha=0.05 and standard deviation at 24 months of 30%, 70 subjects completing ESG would have 98% power to detect an effect of 25% reduction in %EWL.

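### The crossover test has two nulls: a fixed 10% EWL in 7.1 and the same patients' first-year loss in 7.2.2, and the second is selected on its own outcome

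*Combined protocol and SAP*

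**What the plan says.** Section 7.1 sets a one-sample, openly non-randomized hypothesis for controls who move to Level 2: that "of those offered ESG at 12 months, average change in %EWL will be at least 10" percent. The sizing is "Based on a one-sample t-test with two-sided alpha=0.05 and standard deviation at 24 months of 30" percent, and the result is that "70 subjects completing ESG would have 98% power to detect an effect of 25% reduction in %EWL". The same section plans the primary comparison with 25% EWL on ESG "compared to 10% EWL on LS alone with SD of 5" percent. On who continues, it says "we anticipate up to 20% will achieve a successful decrease of" 25% EWL or more on lifestyle alone, and "we anticipate up to 20% may be lost to follow up or drop out prior to 12 month follow up". That leaves 77 of 120 to be offered ESG.

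Section 7.2.2 describes a different test. The 12-to-24-month %EWL of the control patients "will be compared to percent EWL in the same group with lifestyle intervention only in the first 12 months using a one sample t-test". It does not say whether the first-year value is each patient's own (a paired test) or a group mean treated as a constant. Its next paragraph, on initial versus delayed ESG, warns that the comparison is not randomized because LS patients at or above 25% EWL are not followed further. The crossover test carries no such warning.

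Section 5.5 (Control group) gives a third account of who crosses over. It requires attendance at 75% of visits, and joins its two weight criteria (25% EWL not reached; BMI still 30 to 40) with the word or.

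**The concern.** There are two separate problems. First, the hypothesis that is stated and powered is not the one that the analysis section tests. A reader of the results could not tell which null was meant.

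Second, the 7.2.2 comparator is conditioned on itself. A year-2 value exists only for patients who stayed below 25% EWL in year 1, and year-1 %EWL is the yardstick. Cutting off the upper tail can only lower that mean relative to the whole LS arm. Some of the patients left had a poor year by chance and would tend to do better in a second year whatever was done. At stake is how much of a year-2 gain can be credited to ESG.

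**Working it through.** **1. The plan's own figure.** One-sample t-test, n = 70, SD 30, two-sided 0.05, difference 25 − 10 = 15: noncentrality 15/30 × √70 = 4.18, power 98.5%. The stated 98% reproduces. With a null of 0 the power would exceed 99.99%, so the figure rests on a null of 10. The patient count also reproduces: 120 × 0.8 × 0.8 = 76.8.

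**2. Does the power survive under 7.2.2?** Take a paired test with year-1 mean 10 and SD 5, year-2 mean 25 and SD 30, and year-to-year correlation r. The SD of the difference is √(30² + 5² − 2r × 30 × 5), which is 30.4 at r = 0 and 27.8 at r = 0.5. Power with 70 patients is 98.2% to 99.4%.

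**3. How far the comparator falls.** Assume year-1 %EWL is normal with mean 10 and SD s, cut off at 25. With z = 15/s and λ = φ(z)/Φ(z), the mean of those left is 10 − sλ. The section 7.1 SD of 5 gives z = 3 and a responder rate of 0.13%. To get 20% responders with mean 10 needs z = 0.842, so s = 15/0.842 = 17.8. Then λ = 0.280/0.8 = 0.350 and the shift is 17.82 × 0.350 = 6.24. Keeping SD 5 and forcing 20% responders instead needs a mean of 20.8; the comparator is then 19.0, a shift of 1.75. The rates of 5% and 10% in the table below are assumptions below the section 7.1 ceiling.

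**4. What regression to the mean does to a paired test.** Suppose ESG adds nothing and year-2 losses keep the LS mean and SD, with correlation r. The expected difference is (1 − r) × shift. Its variance per patient is (1 − r)²v + (1 − r²)s², where v = s²(1 − zλ − λ²).
- 20% responders, r = 0: v = 317.6 × (1 − 0.2945 − 0.1225) = 185.2; variance 185.2 + 317.6 = 502.8, SD 22.4; noncentrality 6.24/22.4 × √70 = 2.33. Against a critical value of 1.995, the chance of favouring ESG is about Φ(0.33) = 63%.
- 20% responders, r = 0.8: difference 1.25; variance 0.04 × 185.2 + 0.36 × 317.6 = 121.7, SD 11.0; noncentrality 0.95; chance about Φ(−1.05) = 15%.

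Simulation agrees: about 63%, 46%, 33% and 15% for r = 0, 0.3, 0.5 and 0.8. The same steps give the other rows.

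| LS responders | SD needed | Comparator | Shift | Falsely favours ESG, r = 0.8 to r = 0 (nominal 2.5%) |
|---|---|---|---|---|
| 0.13% | 5 | 9.98 | 0.02 | about 2.5% |
| 5% | 9.1 | 9.0 | 1.0 | about 5% to 10% |
| 10% | 11.7 | 7.7 | 2.3 | about 7% to 23% |
| 20% | 17.8 | 3.8 | 6.2 | about 15% to 63% |

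**5. Section 5.5 read literally.** With an ideal BMI of 25 (section 2.3), a patient with baseline BMI b who loses exactly 25% of excess weight ends at b − 0.25(b − 25). This is 30 or more when b ≥ 23.75/0.75 = 31.7. With baseline BMI assumed uniform on 30 to 40, simulation of the 20% case lets about 72% of responders cross over. The comparator is then 8.3, and the false-favour rate is about 4% to 8%.

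**6. The fixed null in the same no-benefit scenario.** The expected year-2 loss of the selected patients is 10 − r × shift (for example 10 − 0.5 × 6.24 = 6.9), which for r of 0 or more never exceeds 10. A test against 10 is therefore not tilted towards ESG by this selection.

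**The case against.** Much can be said for the plan. This is a secondary analysis in a phase that sections 4.1 and 7.1 label non-randomized, and section 4.2.1 lists the outcome simply as 24-month %EWL. The 10% is also the assumed LS first-year mean, so it may be only a planning value for the 7.2.2 comparator. Section 7.1 nevertheless writes it as the hypothesis.

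With the stated SD of 5 the selection hardly matters, and 20% is an upper bound used to reach a minimum patient count. That stands, but SD 5 with mean 10 implies 0.13% responders, so the two inputs conflict and neither settles the size. The 75% visit rule may select better first-year results, and plateau or regain in a second lifestyle year could work the other way. The documents give no figures for either.

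Three stronger readings are tempting and are not supported:
- *That the 98% power is wrong for the test to be run.* It belongs to the fixed null, but a paired test has 98.2% to 99.4% under the plan's own mean and SDs.
- *That a true post-ESG loss of exactly 10% would be declared a success in 31% to 40% of trials instead of 2.5%.* Those figures take 3.8 as the null, with a contrast SD of 35 to 30. They compare two different hypotheses: if patients truly lost 3.8 and then 10, rejection detects a real difference. With 10% or 5% responders the same calculation gives about 8–9% or 4–5%. No success rule depends on this test.
- *That the whole LS arm's 12-month mean would be a fair comparator.* It would set selected patients against a group that includes the responders who were removed.

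**Conclusion.** The conflict between 7.1 and 7.2.2 is plain on the page and should be resolved. The direction of the selection effect is also clear relative to the LS-arm mean: the year-1 comparator is lowered, and regression to the mean favours year 2.

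Its size is not fixed by the documents. It runs from negligible (0.02 points, SD 5) through 1.0 to 2.3 points (5% to 10% responders) to 6.2 points at the 20% ceiling. A false-favour rate of 15% to 63% applies only to that last case, and falls to about 4% to 8% if section 5.5 is read literally. These figures assume normal losses, 70 patients, a year-2 loss under no benefit with the LS mean and SD, and, for the literal reading, uniform baseline BMI. What is in doubt is the meaning of a positive result; power is not materially affected.

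**What to change.** - In 7.2.2, make the inferential test the one already stated and powered in 7.1: a one-sample t-test of the 12-to-24-month %EWL against 10%, with a line on why 10% is the benchmark.
- Report the year-1 versus year-2 contrast as descriptive, labelled non-randomized and subject to selection and regression to the mean, in line with the caution that 7.2.2 already gives for initial versus delayed ESG.
- Reconcile the account of who crosses over in sections 5.5, 7.1 and 7.2.2, so that the analysed group is defined once.
- Do not substitute the whole LS arm as the comparator.

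Cost: a sentence or two and possibly a higher hurdle. No extra patients or data are needed, and the 98% then belongs to the test that is run.
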